## **PROTOCOL SUMMARY**

Study Title	Safety and effectiveness of transcutaneous electrical nerve stimulation (TENS) of the T6/T7 dermatome in adult, overweight-to-Type 1 obese- subjects (i.e. BMI of between 25 to 35 kg/m² inclusive) when used for weight loss.
Study Coordinating Pls	[name] and [name]
Study Rationale	Previous studies have shown that TENS facilitates weight loss in overweight subjects. The therapy in these trials was delivered using an over the counter device not optimized for daily use for weight loss.
	The present pivotal study will test the hypothesis that daily, wearable TENS is safe and effective for weight loss therapy in overweight- to Type 1 obese-subjects (i.e. BMI of 25 -35 kg/m² inclusive). Secondarily the study will assess the impact of the TENS therapy on appetite. Ancillary endpoints include changes in hemoglobin A1c, changes in ALT, and blood lipids as secondary measures associated with weight loss.
Name of the Device(s) Used in Study	The Elira wearable, patch system.
Description of Components	The Elira wearable patch system is an RF coupled, wearable transcutaneous electrical nerve stimulation (TENS) device controlled via Bluetooth by a smart phone unit running a custom application which directs therapy from the patch within safe limits set by a clinician and also includes a diary. Subjects will be supplied as well with paper diaries for appetite and symptoms along with an electronic scale.
Study Design	Randomized, adaptive parallel arm study. Subjects will be initially screened during a screening period (+/- 7 days). During this screening period, subjects will sign an Informed Consent Form (ICF), have their weight/height and blood pressure measured, take a pregnancy test (females of child bearing potential), get blood drawn for analysis (CMP, blood lipids, hemoglobin A1c), and complete the PHQ-9 and patient preference survey.
	At the end of the screening period, eligible subjects will be enrolled/randomized in the study to either a treatment or control group. After enrolling, both control and treatment subjects will be instructed to follow a healthy 1200 calorie diet for the duration of the study and will receive training on the use of the electronic scale and completion of paper diaries. For the treatment group, subjects will be instructed on use of the Elira wearable, patch system. Following this, subjects will enter the Therapy Period for 12-weeks.
	At the end of the Therapy Period, subjects will complete an end of study visit to be assessed for weight loss, blood pressure, blood lipids, hemoglobin A1c, CMP (Reduction of ALT), patient preference questionnaire and their participation will be considered complete (pending laboratory results, adverse events or serious adverse events).
	The study utilizes an adaptive approach where cohorts of enrolled/randomized subjects (in groups of 25 per arm) are assessed for dose response and progression to achievement of primary and secondary endpoints. Frequent interim endpoint

	assessment utilizing Markov-chain Monte Carlo (MCMC) methods coupled with Longitudinal analyses will be utilized to determine sample sizes for future cohorts (assessed primarily via Normal dynamic linear modeling [NDLM]).
Subject Population / Sample Size	The primary endpoint is powered at a final enrollment of 75 subjects per group, for a total of 150 subjects, but interim analyses based on Bayesian posterior probability distributions with multiple imputation will be utilized to assess interim significance.
	In the event the interim analysis is not significant, up to 300 subjects may need to be enrolled in order to achieve final separation between groups for statistical significance. Thus, Elira may need to screen up to 500 subjects to account for exclusions prior to enrollment.
Study Duration and Sites	Minimum study duration for each patient will be 13 weeks. As it is expected that recruitment of 150 subjects will take up to 12 weeks, the overall study duration is anticipated to be a minimum of 26 weeks, assuming all cohorts are enrolled. The study will be conducted at up to 10 centers.
Inclusion	Subject is between 18 – 65 years of age inclusive.
Criteria	Subject has a BMI of 25-35 kg/ m² inclusive.
	Subject has signed the informed consent form and is able to comply with study protocol and adhere to study visit schedule.
	Subject is able to wear and use a wearable, patch TENS system.
	Subject is able to use a touch screen hand held smart phone.
	Subject is fluent in English and can complete patient questionnaires.
	Subject can comply with a 1200 calorie diet for the duration of the study.
	Subject is male or non-pregnant, non-lactating female, who agrees to use effective contraceptive methods throughout the length of the trial based on PI approval.
	Females of childbearing potential (FOCBP) must have a negative urine pregnancy test at screening or enrollment visit, prior to placement of ELIRA device.
Exclusion Criteria	Subject has any known gastrointestinal disorder that in the opinion of the PI precludes enrollment into the trial.
	Subject has had a prior bariatric procedure or any previous procedure on the stomach.
	Subject has any significant multisystem disease in the opinion of the PI.
	Subject has > 6.5 HbA1c.
	Subject has significant cardiac arrhythmia, ectopy, or significant cardiovascular disease.
	Subject has an existing implanted electrical stimulator (e.g., pacemaker, AICD).
	Subject is a female of child-bearing potential who is pregnant or intends to become pregnant during the trial period.
	Subject has current and/or a history of cancer within the past 5 years (not including basal cell carcinoma or cervical carcinoma in situ).
	Subject has had a weight change of + 5% of his/her Total Body Weight in the 3 months prior to screening.

Subject has a moderate / severe psychiatric disorder.

Subject has a diagnosed neurological disease.

Subject has a diagnosed eating disorder.

Subject has a skin disorder affecting the thoracic dermatomes.

Subject has active or has ever had shingles in the abdominal area.

Subject has abdominal surgery or other scars which may interfere with stimulation in the opinion of the PI.

Subject is currently enrolled in other, potentially confounding research.

Subject has known allergic reaction to materials in the electrodes and/or is otherwise unable to tolerate stimulation with the wearable TENS system.

Subject is actively participating or unwilling to discontinue participation in another weight loss program.

Subject is taking weight loss control medications including but not limited to OTC medications, Metformin, and Belvig.

Subject is unable to take anti-nausea medications planned for the study.

Inability to walk at least 0.8 kilometers per day (10 minutes of continuous walking).

Current smoker or user of nicotine product or smoking cessation within 1 year of the screening date.

History of treatment for or current abuse of drugs or alcohol.

A score of ≥10 on the Patient Health Questionnaire 9 (PHQ-9), demonstrating moderate depression.

[figure not shown]
Any subject that the investigator considers inappropriate for the study for medical reasons.

Subject has a history of moderate/severe migraines or severe headache disorders requiring the treatment of Topiramate.

Subject has a history of migraines or severe headache disorders requiring the treatment of Topiramate.

Subject is on drug therapy which may alter antral motility or appetite, per PI discretion (Appendix 8).

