#### 5. STUDY DESIGN

Randomized, adaptive parallel arm study. Subjects will be initially screened during a screening period (1 week, ±7 days; Figure 2). During this screening period, prior to study procedures being performed, subjects will sign an informed consent form. Then they will have their

[figure not shown]

Figure 2: Study Outline

weight and blood pressure measured, FOCBP will have a pregnancy test, get blood drawn for analysis (blood lipids, CMP, hemoglobin A1c), and complete patient preference questionnaires. At the end of the screening/baseline period, eligible subjects will be offered the chance to enroll in the study. After enrolling, subjects will be randomized to treatment or control groups.

The Treatment group will be instructed to follow a healthy 1200 calorie diet that they will follow for the duration of the study and will receive training on the use of the weekly paper diary, electronic scale, smartphone app and the Elira wearable patch system. All treatment subjects will be required to stimulate in the office for a period of time to confirm sufficient system training and tolerability of the stimulation. Following this, subjects will enter the Therapy Period, for a 12-week duration.

The Control group will be instructed to follow a healthy 1200 calorie diet that they will follow for the duration of the study and will receive training on the use of the weekly paper diary and electronic scale. The Control group will not receive the electronic smartphone app or the Elira wearable patch system.

At the end of the Therapy Period, subjects will be assessed for weight loss, blood pressure, CMP, blood lipids, HbA1c, and will be terminated from the study.

The study utilizes an adaptive approach where cohorts of enrolled subjects (in groups of 25 per arm) are assessed for dose response and progression to achievement of primary and secondary endpoints. Frequent interim endpoint assessment utilizing Markov-chain Monte Carlo (MCMC) methods coupled with longitudinal analyses will be utilized to determine sample sizes for future cohorts (assessed primarily via Normal dynamic linear modeling [NDLM]).

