#### 8.2 JUSTIFICATION OF SAMPLE SIZE

The calculated sample size for the study is based on conservative imputation of results from other studies on weight loss including the use of TENS for weight loss. The degree of coaching/dietary support throughout the present study is moderate intensity lifestyle/weight coaching. The sample size modeling assumes an average of 3.5% TBWL in Control subjects using diet and exercise alone. The estimated weight loss in the Treatment subjects is modeled from preliminary data on T6/T7 dermatomal TENS when used for weight loss: 7.5% TBWL. The variance of the responses in the study (i.e. Standard Deviation) was modeled at + 5% TBWL. This value was taken from previous dermatomal TENS weight loss study results. The model assumes a 30% drop out rate across groups and an 80% powered endpoint using an adaptive p spending model wherein interim posterior probability assessments are allowed after enrolling proscribe cohorts of not less than 25 subjects per group for not less than 7 weeks of stimulation. The alpha penalty will be minimized per interim by assessing the relationship between stimulation (i.e. dose) and weight loss using Normalized Linear Dynamic Modeling (NLDM) to determine overall sample size projected (i.e. futility) rather than assessing the primary endpoint hypothesis per se. Monotonicity will not be assumed in this analysis. This modeling provides an estimate of 75 subjects per group, for a total study size of 150 subjects. However, the protocol allows for enrollment of additional subjects should the interim model project under powering of the primary endpoint.

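### The Protocol Summary and section 8.2 give the interim analyses different purposes and different extension triggers, and no alpha, number of looks, boundary or posterior threshold is stated, so type I error cannot be verified

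*Combined protocol and SAP*

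**What the plan says.** Protocol Summary, Subject Population / Sample Size: the trial is powered at 75 per group, but "interim analyses based on Bayesian posterior probability distributions with multiple imputation will be utilized to assess interim significance". It continues: "In the event the interim analysis is not significant, up to 300 subjects may need to be enrolled in order to achieve final separation". The Study Design row of the same summary adds that interim modelling will set the sizes of future cohorts, mainly by normal dynamic linear modelling (NDLM).

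Section 5 repeats the NDLM statement. It also says that cohorts of 25 per arm "are assessed for dose response and progression to achievement of primary and secondary endpoints".

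Section 8.2 describes "an 80% powered endpoint using an adaptive p spending model wherein interim posterior probability assessments are allowed", after "cohorts of not less than 25 subjects per group for not less than 7 weeks of stimulation". It then says: "The alpha penalty will be minimized per interim by assessing the relationship between stimulation (i.e. dose) and weight loss", so as to project overall size or futility "rather than assessing the primary endpoint hypothesis per se". Finally, "the protocol allows for enrollment of additional subjects should the interim model project under powering of the primary endpoint". No upper limit is given there.

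The Statistical Analysis part of the Protocol Summary and section 8 both plan 95% two-sided intervals. Only the former adds a general remark on correcting for multiplicity. Both use posterior distributions to assess efficacy within and between cohorts.

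**The concern.** The purpose of the interim (significance test or projection) and the trigger for enrolling more subjects (non-significance or projected under-powering) differ between the two places, and only one gives a cap. Two analysts could each follow the plan and act differently on the same data. One might claim success at an interim, or extend because the result was not significant; the other might do neither.

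The protocol calls this study pivotal and runs it open label (section 5.3), so arm-level results may be visible when the extension is decided. If efficacy is tested repeatedly without adjustment, the false-positive rate exceeds its nominal level. A rule written after data have been seen would not repair that credibly.

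Section 8.2 also bases the projection on dose, and dose is not assigned at random.

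**Working it through.** **1. The texts side by side**

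| Item | Protocol Summary | Section 8.2 |
|---|---|---|
| Purpose of interim | Assess significance; also set cohort sizes by NDLM | Project size or futility from the dose model; also posterior assessments with an alpha penalty |
| Trigger for extension | Interim not significant | Model projects under-powering |
| Cap | 300 | None given |
| Alpha, number of looks, boundary, threshold | None | None (p spending named only) |

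**2. Can alpha be recovered from the sample size?** Section 8.2 gives means of 7.5% and 3.5% (difference 4), SD 5, 80% power, 30% dropout and 75 per group. At an assumed two-sided 5%:

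n = 2 × SD² × (z₁ + z₂)² / difference² = 2 × 25 × (1.960 + 0.842)² / 16 = 24.5, so 25 completers; 25 / 0.7 = 35.7, so 36 enrolled per group.

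The stated 75 is not reproduced. Two-sided alpha of 0.01 gives 53 per group (37 / 0.7) and 0.001 gives 78 (54 / 0.7). The sample size therefore does not reveal the alpha or the spending rule.

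**3. Type I error under different readings.** Assumptions: two-sided 5%, 300 read as the total (150 per arm), complete week-12 outcomes at each look. Under the null, the Z statistics at n_j and n_k per arm have correlation √(n_j / n_k). Equal dropout at every look leaves this unchanged. The probability that any |Z| reaches 1.96 is:
- looks at 75 and 150 per arm (correlation √0.5 = 0.707): 8.3%
- looks at 25, 50 and 75: 10.7%
- six looks, every 25 up to 150: 15.5% by numerical integration, 15.3% in 400,000 simulated trials
- spending applied, futility-only looks, or no interim efficacy test: about 5%

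One qualification applies to the last line. If there is no interim claim but the size is changed on the between-arm difference itself, an unadjusted final test can reach 5.8% (decision at 25 per arm) to 6.6% (at 50) in the worst case.

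**4. What a stated boundary would give.** O'Brien-Fleming limits of 2.797 at 75 and 1.977 at 150 per arm give 5.0% overall (nominal p 0.0052 and 0.048). With 75 × 0.7 = 52.5 completers per arm, the expected first-look Z under the plan's assumptions is 4 / (5 × √(2 / 52.5)) = 4.10. First-look power is then Φ(4.10 − 2.797) = 0.90. Overall power is 0.82 even if the SD were 10.

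**5. The dose relation.** Section 5.1 lets treated subjects drop a session for tolerance, or add rescue sessions when appetite suppression is insufficient. Dose is therefore partly a result of response. The within-arm slope of weight loss on dose is confounded, in a direction that cannot be known beforehand, and it is not the between-arm difference that the trial is sized to detect.

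**The case against.** The strongest defence is that the texts describe one hybrid: NDLM governs size, and p spending governs any posterior assessment of efficacy. The Protocol Summary does carry the NDLM sizing rule, and section 8.2 does allow posterior assessments and speaks of an alpha penalty. This stands to the extent that the contrast is not a pure test against a pure projection. It does not reconcile the two triggers, and it supplies none of the missing values.

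The 95% two-sided intervals and the multiplicity remark suggest an intended 5% level with some control. They are not tied to the interim looks, and the remark is missing from section 8.

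Two stronger readings are tempting:
- A reader might infer that the trial runs at 8% to 15% type I error. The documents do not support this. Those figures assume unadjusted testing, while section 8.2 names spending. Six looks is also an assumption: cohorts have a minimum size, but the number of looks is not given.
- A reader might infer that the confounded dose slope itself inflates type I error, or biases the extension in a known direction. Neither follows. With normal outcomes, a slope estimated within the treated arm alone is separate from the arm mean, and section 5.1 permits dose changes both ways. The plan does not say whether controls enter the model. The supported point is that the slope is a poor sole guide to size or futility.

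**Conclusion.** The concern holds. The plan gives two interim purposes and two extension triggers, each text mixing both roles, and no stated quantity fixes the error rate. The supported statement of size is a range: at an assumed two-sided 5%, from about 5%, through 8.3% (unadjusted looks at 75 and 150 per arm), to about 15% (six unadjusted looks). This range shows how much depends on the missing rule; it does not estimate the trial's actual error rate. Because it bears on the primary conclusion of a pivotal, open-label trial, it should be settled before any interim data are examined.

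**What to change.** Bring the Protocol Summary and sections 5, 8 and 8.2 to one rule, and state alpha (for example two-sided 5%). Two workable forms:

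**(a) No interim efficacy claim.** Remove the non-significance trigger. Re-estimate size once from the one-sample SD of %TBWL ignoring arm labels, then make one final test. Enrolled per arm = 0.981 × SD² / 0.7, where 0.981 = 2 × (1.960 + 0.842)² / 4², with minimum 75 and maximum 150. As the trial is open label, name the role that computes it. Define the trigger, using accrual of 150 / 12 = 12.5 per week:
- 25 enrolled per arm followed to week 12: 25 × 0.7 = 17.5, about 18 completers per arm; 50 / 12.5 + 12 = week 16.
- 25 completers per arm: 25 / 0.7, about 36 enrolled per arm; 72 / 12.5 + 12 = about week 18.

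Cost: no early efficacy claim. Both dates fall after the planned end of enrolment at week 12, so state whether enrolment pauses. With the cap at 150, the rule has about 77% power if the SD is 10.

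**(b) Keep the extension to 300 as a group-sequential rule.** Fix looks at 75 and 150 per arm on week-12 outcomes, with |Z| ≥ 2.797 and 1.977 and matching adjusted intervals, or a posterior threshold calibrated by simulation to the same alpha. Recalibrate if a look uses earlier or imputed outcomes.

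Cost: a final p limit of 0.048, and a short simulation report if the threshold is Bayesian. Week-12 data on all 150 arrive at about 12 + 12 = week 24, so state whether enrolment pauses for about 12 weeks.

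If the 25-per-arm looks are kept, include them in the spending function or limit them to non-binding futility. In all cases, label the within-arm dose-response analysis exploratory, and do not let it alone decide sample size or futility.

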## Dosing Regime

Treatment subjects will be trained in rotation of the patch electrodes every 24h such that it is applied to varying locations on the T6/T7 dermatome. Each treatment subject will receive up to 30 mA of sustained current stimulation (up to 40mA peak) for 30 minutes after each of three meals per day (delivered within 1-hour post prandially). Based on tolerance of the therapy, a subject may decrease his or her dose by dropping one of the 3 post prandial sessions after receiving approval from a clinical coordinator and/or PI. Subjects who do not experience sufficient appetite suppression may add 15-minute pre-prandial rescue sessions delivered within 2 hours before each meal after receiving approval from a clinical coordinator and/or PI. The nominal stimulation dose per day for any subject will thus be 2400 mA (60 minutes at 40 mA) while the maximum dose for any given subject will be 5400 mA (135 minutes at 40 mA).

#### Visit Schedule

Screening/Baseline Visit 0 (-1 week; ± 7 days) – Obtain Informed Consent prior to any study procedures. Confirm subject has met all inclusion criteria and no exclusion criteria. History & Physical including height & weight, diet history, baseline clinical parameters, provide laboratory requisition, urine pregnancy test for women of childbearing potential (WOCBP), and questionnaires. Initiate subject weekly paper diary with training for weekly completion. Subjects will be instructed to return with their weekly paper diary(ies) at their next scheduled visit.

**Enrollment/Randomization Visit 1 (Day 0; ± 7 days)** – Confirm subject continues to meet all inclusion criteria and no exclusion criteria. Assessment of T6/T7 dermatomes, clinical parameters, BP, weight, perform urine pregnancy test for WOCBP if not done at screening, administer TFEQ-R18V2 Questionnaire, assess for adverse events and changes to concomitant medications. Subjects will be randomized based on the blocked randomization algorithm.

Treatment and Control subjects will be instructed to follow a healthy 1200 calorie diet throughout the study, an electronic scale with instructions on use will be provided, and a paper diary with training for weekly completion will be provided. Subjects will be instructed to return with their paper diary(ies) at the next scheduled visit.

Only the treatment subjects will receive a handheld smartphone with the custom application and an Elira wearable patch system. It is recommended for treatment subjects to utilize an TENS Clean-Cote Skin Wipes and/or alcohol prep pad to maintain a clean application area for the treatment. Treatment subjects will also receive Cetaphil Moisturizing Lotion to be used if any irritation occurs at the treatment site. Subject will

be instructed to notify site immediately if any irritation occurs. Treatment subjects will stimulate under the supervision of the investigator or coordinator for 30 minutes prior to being discharged with the device. Treatment subjects will be assessed for toleration of the stimulation to further evaluate dose adjustment. Treatment subjects will be discharged with the Elira wearable patch system & Smartphone App and instructions on use. Treatment subjects will be instructed to return with the Elira wearable patch system and smartphone app at their next scheduled visit.

Therapy Phase Visits 2, 3 & 4 (week 1, 4, 8 respectively; + 7 days) – Treatment and Control subjects will be assessed for adverse events and changes to concomitant medications. Obtain BP and weight. Administer the TFEQ-R18V2 Questionnaire. Collect and review paper diaries, dispense new paper diaries and review instructions for weekly completion. All subjects will be encouraged to follow a healthy 1200 calorie diet throughout the study. Subjects will be instructed to return with their paper diaries at their next scheduled visit.

Treatment subjects will be assessed for any adverse device effects (ADE), T6/T7 dermatome assessment, review and download of diary data, and stimulation adjustment (if needed). Treatment subjects will be discharged with the smartphone application and the Elira wearable patch system and instructions on use. Treatment subjects will be instructed to return with the Elira wearable patch system and smartphone app at their next scheduled visit.

End of Study Visit 5 (week 12; ± 7 days) – Treatment and Control subjects will be assessed for adverse events and changes to concomitant medications. Physical including weight, BP, requisition for laboratory tests, urine pregnancy test for WOCBP, and completion of questionnaires (PHQ9, TFEQ-R18V2, and Patient Preference Survey). Collect and review paper diaries.

Treatment subjects will return the Elira wearable patch system and the smartphone application. Treatment subjects will be assessed for ADEs and have their T6/T7 dermatome area examined.

